4.4 VISIT WINDOWS

Visit windows will only be applied to scheduled time points for laboratory parameters. This will include full blood hematology and chemistry assessments at Day 1 and Day 10, and blood liver chemistry assessment before dosing with the study treatment on Day 1, Day 4 and Day 7 (if study treatment is planned on Day 7) (Table 2). No other visit windows will be used in the study analysis.

Table 2 Acceptable Time Windows – Laboratory Parameters

Time Point (Scheduled Time Point)	Acceptable Time Window
Visit 1 (Day 1)	pre-dose Day 1
Visit 4 (Day 4)	Between Day 3 and Day 5 as follows: -if patient presents on Day 4 this will be classed as Visit 4; -if patient presents on Day 3 with no Day 4, and no Day 5 this will be classed as Visit 4; -if patient presents on Day 5 with no Day 4, and no Day 3 this will be classed as Visit 4; provided this is the day study treatment was received.
Visit 6 (Day 7)	Between Day 6 and Day 8 as follows: -if patient presents on Day 7 this will be classed as Visit 6; -if patient presents on Day 6 with no Day 7, and no Day 8 this will be classed as Visit 6; -if patient presents on Day 8 with no Day 7, and no Day 6 this will be classed as Visit 6; provided this is the day study treatment was received, per protocol guidance.
Visit 7 (Day 10)	Between Day 8 and Day 12

Measurements collected within the acceptable time window for each scheduled assessment time point, including data obtained at the time of withdrawal, will be used for the analyses at each assessment time point. For all patients with multiple values within a visit window, the value obtained closest to the target time point (Day 1 and Day 10) will be used for the full blood chemistry and haematology evaluations. The value obtained prior to the target time (Day 4 and Day 7) will be used for the pre-study treatment blood liver chemistry. The assessment time point having no measurements within the corresponding acceptable time window will be considered as missing.

For summaries of data not collected by visit, such as adverse events, medical history and concomitant medications, all data up to the end of study will be included.

4.5 EFFICACY ANALYSIS

Efficacy analyses will be conducted for the mITTI population. Hypothesis tests will be two-sided at the 5% significance level, unless stated otherwise.

To manage the overall type I error, the primary and key secondary endpoints will be tested sequentially. The order of testing will be as follows:

- TTCl
- Response rates of the 6-point ordinal scale at Day 7
- Time to Clinical Response

If the primary efficacy analysis hypothesis test result is not statistically significant (i.e. $p > 0.05$), the hypothesis below that result in the hierarchical chain will be considered exploratory and no claims of statistical significance will be made. The same rules apply to the next endpoint in the chain.

4.5.1 **Primary Efficacy Endpoint**

The primary efficacy objective for this study is to evaluate the efficacy of baloxavir marboxil plus a SOC NAI, compared with matching placebo plus SOC NAI based on the following endpoint:

- TTCI (defined as time from treatment start to hospital discharge or time to NEWS2 ≤ 2 and maintained for 24 hours, whichever comes first)

TTCI is calculated as per [Table 3](#).

Table 3 TTCI Calculations

TTCI based on	TTCI (hours)
NEWS2 ≤ 2 for 24 hours	date time of initial NEWS2 assessment ≤ 2 - start treatment date time
NEWS2 ≤ 2 prior to discharge*	date time of initial NEWS2 assessment ≤ 2 - start treatment date time
Hospital discharge	date time of hospital discharge - start date time of treatment

*when a patient met the NEWS2 ≤ 2 and was discharged from hospital during the 24 hour period of stability confirmation, the time of achieving TTCI was defined as the initial time at which the NEWS2 ≤ 2 and not the time of hospital discharge.

NEWS2 (National early warning score 2) is the sum of the score of each of the following assessments, as described in [Appendix 4](#): respiration rate (per minute), oxygen saturation (SpO₂%) according to scale 1 or scale 2, supplemental oxygen or room air, systolic blood pressure (mmHg), pulse rate (bpm), consciousness level, temperature (°C).

Missing data for the calculation of the NEWS2 will not be imputed for the following reasons:

1. TTCI endpoint can be met through hospital discharge.
2. The physiological components of the NEWS2 can be highly heterogeneous in the study patient population and therefore the process of imputation would not be relevant.

The TTCI will be compared between the baloxavir marboxil plus SOC NAI and matching placebo plus SOC NAI arms using the stratified log-rank test within three regions (i.e. North America, EMEA, ROW), NEWS2 score at baseline (≤ 7 , > 7), and time from symptom onset to study treatment (≤ 48 hours, > 48 hours) included as the stratification factors. The Kaplan Meier plot, median time to response, 95% CIs, and p-values will be presented.

The log-rank test is most appropriate when the assumption of proportional hazards is met. The proportional hazards assumption will be tested graphically using the log cumulative hazard plot by treatment group. The plots for each treatment group will be parallel if the proportional hazard assumption holds. Should the proportional hazards assumption be violated, the Gehan Wilcoxon test will be used to analyze the data.

The estimand is the difference in distributions between baloxavir marboxil plus SOC NAI and matching placebo plus SOC NAI arms in the mTTi for the TTCI using appropriate method, as described above. This absolute measure will be assessed over the duration of the study (35 days). The median TTCI for each treatment group and difference between treatment groups will be presented. Intercurrent events are those that occur after treatment initiation and either preclude observation of the variable or affect its interpretation. Intercurrent events, such as patients who are lost to follow-up, die or discontinue for any reason prior to achieving a clinical improvement or do not have a clinical improvement event, will be accounted for through censoring rules, as described in [Table 4](#) below.

Table 4 TTCI and Censoring

Event	Censor	Date and Time
Clinical improvement (based on NEWS2 \leq 2 for 24 hours)	No	vital signs assessment where NEWS2 \leq 2 at start of 24 hour period
Clinical improvement (based on NEWS2 \leq 2 prior to discharge)	No	first vital signs assessment where NEWS2 \leq 2 prior to discharge
Clinical improvement (based on hospital discharge)		
- hospital discharge and hospital re-admission within 24 hours) and discontinue study on same day	Yes	hospital discharge
- hospital discharge and hospital re-admission within 24 hours) and continue study	Yes	hospital discharge
- hospital discharge against medical advice (i.e. self-discharge)	Yes	hospital discharge
- all other hospital discharge	No	hospital discharge
Death prior to achieving a clinical improvement	Yes	last vital signs assessment prior to death
Discontinuation for any reason prior to achieving a clinical improvement	Yes	last vital signs assessment prior to discontinuation
Lost to follow-up	Yes	last vital signs assessment
No clinical improvement	Yes	last vital signs assessment

TTCI= Time to clinical improvement; NEWS2= National early warning score

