4.5.4 Vital Signs

Vital signs will include measurements of respiratory rate, pulse rate, peripheral oxygen saturation, systolic and diastolic blood pressures, and body temperature. Body temperature should be measured using the same methodology throughout the study.

For patients requiring supplemental oxygen, the oxygen flow rate (L/min) and/or fraction of inspired oxygen (FiO_2) should be recorded.

All of the vital sign parameters should be recorded *together* four times per day for the duration of the hospitalization throughout the treatment period (Day 1/Visit 1 to Day 10). It is recommended that the collection timepoints for vital signs and assessments (specific to NEWS2, Section 4.5.4) are spread throughout the study day to reflect the patient's condition over the entire study day, where possible. Following hospital discharge during the treatment period (Day 1 to Day 10) these parameters should be recorded once at each return visit to the clinic. Patients who remain hospitalized during the follow-up period (Day 11+) require daily collection of vital signs for the purpose of the study. During the follow-up period in patients who have been discharged, vital sign measurements and temperature are to be recorded at the investigators' discretion (e.g., if symptoms and signs persist during follow-up). Vital sign measurements may be performed by an MN professional.

4.5.5 Assessments Specific to National Early Warning Score 2

In addition to the vital measurements, the patient's consciousness level and the presence or absence of respiratory support must be recorded. The NEWS2 parameter for respiratory support is the selection of either air or oxygen –“oxygen” can include other forms of ventilation to maintain oxygen saturation (see [Appendix 3](#)).

These should be recorded at the same time points as the vital sign measurements (see Section 4.5.4 and [Appendix 1](#)).

4.5.6 National Early Warning Score 2

The NEWS2 should be calculated by the site at screening only based upon vital sign values and assessments related to National Early Warning Score 2 (see Section 4.5.5) recorded during the patient assessment. Should these assessments be conducted more than once during the screening period (per site patient care), all data collected closest to but before randomization should be used for the NEWS2 score calculation and assessment of patient eligibility. See [Appendix 3](#) for calculation instructions.

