A and B and (2 of C, D and E) met for 24 hours	date time of initial vital signs assessment where 4 out of 5 criteria initially met and subsequently maintained for 24 hours - start treatment date time
A and B and (2 of C, D and E) met prior to discharge*	date time of initial vital signs assessment where 4 out of 5 criteria initially met and subsequently discharged - start treatment date time
Hospital discharge	date time of hospital discharge - start date time of treatment

TTCR=Time to Clinical Response.

*when a patient met vital sign criteria and was discharged from hospital during the 24 hour period of stability confirmation, the time of achieving TTCR was defined as the initial time at which vital signs were resolved and not the time of hospital discharge.

The time to clinical response will be compared between the baloxavir marboxil plus SOC NAI and matching placebo plus SOC NAI arms using the stratified log-rank test within three regions (i.e. North America, EMEA, ROW), NEWS2 at baseline (≤ 7 , > 7), and time from symptom onset to study treatment (≤ 48 hours, > 48 hours) included as the stratification factors. The Kaplan Meier plot, median time to response, 95% CIs, and p-values will be presented.

The log-rank test is most appropriate when the assumption of proportional hazards is met. The proportional hazards assumption will be tested graphically using the log cumulative hazard plot by treatment group. The plots for each treatment group will be parallel if the proportional hazard assumption holds. Should the proportional hazards assumption be violated the Gehan Wilcoxon test will be used to analyze the data.

The estimand is the difference in distributions between baloxavir marboxil plus SOC NAI and matching placebo plus SOC NAI arms in the mITTi for the time to clinical response, using appropriate method, as described above. This absolute measure will be assessed over the duration of the study (35 days). The median TTCR for each treatment group and difference between treatment groups will be presented.

Intercurrent events are those that occur after treatment initiation and either preclude observation of the variable or affect its interpretation. Intercurrent events, such as patients who are lost to follow-up, die or discontinue for any reason prior to achieving a clinical improvement or do not have a clinical improvement event, will be accounted for through censoring rules, as described in [Table 7](#) below.

Table 7 TTCR and Censoring

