Event	Censor	Date and Time
Clinical Response (based on vital signs assessments)	No	first vital signs assessment where 4 out of 5 criteria initially met and subsequently maintained for 24 hours period
Clinical Response (based on vital signs criteria met prior to discharge)	No	first vital signs assessment where 4 out of 5 criteria initially met and maintained prior to discharge
Clinical Response (based on hospital discharge)		
- hospital discharge to another hospital (i.e. hospital admission within 24 hours) and discontinue study on same day	Yes	hospital discharge
- hospital discharge to another hospital (i.e. hospital admission within 24 hours) and continue study	Yes	hospital discharge
- hospital discharge against medical advice	Yes	hospital discharge
- all other hospital discharge	No	hospital discharge
Death prior to achieving a clinical response	Yes	last vital signs assessment prior to death
Discontinuation for any reason prior to achieving a clinical response	Yes	last vital signs assessment prior to discontinuation
Lost to follow-up	Yes	last vital signs assessment
No clinical response	Yes	last vital signs assessment

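### The rule that makes an unconfirmed NEWS2 of 2 or less an event when discharge follows within 24 h does not exclude the discharges the SAP otherwise censors

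*SAP*

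**What the plan says.** **TTCI (SAP 4.5.1).** The endpoint is the earlier of hospital discharge and a NEWS2 of 2 or less held for 24 h. The Table 3 footnote covers a patient who reaches the threshold and leaves before the hold is complete. If that patient "was discharged from hospital during the 24 hour period of stability confirmation, the time of achieving TTCI was defined as the initial time" of the reading, the event is backdated to it. Row 2 of Table 4 repeats this as uncensored, dated at the "first vital signs assessment where NEWS2" is 2 or less. Neither place limits the type of discharge.

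Further down Table 4, under the heading for improvement based on hospital discharge, three entries are censored at discharge:
- "hospital discharge and hospital re-admission within 24 hours) and discontinue study on same day";
- the same discharge and re-admission where the patient continues in the study;
- "hospital discharge against medical advice (i.e. self-discharge".

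Every other discharge is an event.

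**TTCR (SAP 4.5.2.3).** The Table 6 footnote is parallel, for anyone who had satisfied the required thresholds but then "was discharged from hospital during the 24 hour period of stability confirmation, the time of achieving TTCR was defined as the initial time" of meeting them. Row 2 of Table 7 is uncensored at the "first vital signs assessment where 4 out of 5 criteria initially met and maintained prior to discharge". The censored entries, again only under the discharge heading, are discharge against medical advice and transfer, worded as "hospital discharge to another hospital (i.e. hospital admission within 24 hours) and discontinue study on same day" with a counterpart for patients who continue.

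**Time to NEWS2 of 2 or less (SAP 4.5.3, Table 11).** There is an uncensored row for the threshold met before discharge, also unrestricted, but no discharge rows.

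**The concern.** Row 2 lets discharge stand in for the part of the 24 h hold that was not observed. That makes sense when the discharge would itself count as improvement. For self-discharge and for discharge with hospital admission within 24 h, the SAP has decided that the discharge is not an event. Accepting the same discharge as confirmation of a single reading is inconsistent with that decision, because neither route to the endpoint has been met: the hold is incomplete and the discharge is one that is not counted.

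The situation can easily arise. Protocol 4.5.4 has vital signs recorded "four times per day for the duration of the hospitalization throughout the treatment period", so about 6 h apart if evenly spread, and one qualifying reading shortly before a patient leaves is plausible. The primary endpoint and a key secondary endpoint are both affected. If such departures differ between arms, early events unrelated to recovery would be added unequally.

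**Working it through.** **1. One patient, the rows side by side.** NEWS2 is above 2 until a reading of 2 at 48 h after first dose. The patient self-discharges at 54 h. The hold would have needed to run to 48 + 24 = 72 h.

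| Rule | Result |
|---|---|
| Table 3 footnote; Table 4 row 2 | Event at 48 h |
| Table 4 self-discharge row | Censored at 54 h |
| Same patient without the reading at 48 h | Censored at 54 h (only the self-discharge row applies) |

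The earliest-of definition points to the event at 48 h. No sentence gives an order of precedence. SAP 4.5.1.1 lists analyses for discontinuation, confounding, death as a competing event and artificial support; none covers this case.

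**2. The plan's own figures.** Inputs from Protocol 6.1 and SAP 2.4 and 2.5.1: 176 and 88 patients, control median 94 h, difference 31 h (so 63 h on active), 840 h follow-up, 5% two-sided, 75% RT-PCR positive, 4% dropout, futility look at 65% of events. Exponential times are assumed.
- Randomized: 264/0.75/0.96 = 366.7 (plan: about 366).
- Hazard ratio: 94/63 = 1.492. Events: 176 × (1 − 2^(−840/63)) + 88 × (1 − 2^(−840/94)) = 263.8.
- Drift: √(263.8 × 2/9) × ln 1.492 = 3.064. Power without an interim: Φ(3.064 − 1.96) = 86.5%.
- Beta spent at the look: 0.2 × ln(1 + (e − 1) × 0.65) = 0.150. The bound is one-sided p = 0.076 (plan: about 0.077). Power if the futility rule is followed is 80.2% (plan: at least 80%).

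**3. Events lost if these patients are censored.** The documents give no frequency, so the shares are assumptions.

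| Share of 264 moved to censored | Events left | Power, no interim | Power, futility rule followed |
|---|---|---|---|
| 1% (2.6) | 261.2 | 86.2% | 80.0% |
| 2% (5.3) | 258.5 | 85.8% | 79.7% |
| 5% (13.2) | 250.6 | 84.8% | 79.1% |
| 10% (26.4) | 237.4 | 82.8% | 77.8% |

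This treats every lost event as carrying the full treatment effect, so it is a pessimistic view of the cost.

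**4. Simulation of the two codings.** 4,000 trials per scenario, unstratified log-rank test, no interim, exponential times. An assumed share of each arm has such a discharge, uniformly between 24 and 96 h, and is affected only if not yet improved. All affected patients are assumed to have an unconfirmed reading in the preceding 24 h, unrelated to treatment.

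| Share, active / placebo | Power, censored | Power, event | Null rejection, censored | Null rejection, event |
|---|---|---|---|---|
| 0% / 0% | 85.5% | 85.5% | 5.6% | 5.6% |
| 5% / 5% | 84.9% | 83.8% | 5.0% | 4.6% |
| 5% / 10% | 83.2% | 73.9% | 5.5% | 6.8% |
| 10% / 5% | 84.3% | 88.1% | 4.7% | 5.3% |

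Monte Carlo error is about 0.6 points for power and 0.4 for null rejection. At 5% in each arm with the planned effect, about 7.5 patients per trial are affected. Where the shares differ, counting these patients as events pushes the test towards the arm with more such departures: under the null the mean z is −0.31 at 5% / 10% and +0.27 at 10% / 5%.

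**The case against.** The best defence is that row 2 is deliberate. Protocol 3.3.4 regards a NEWS2 of 2 or less as likely to reflect meaningful improvement and possible fitness for discharge. A self-discharged patient with such a reading has objective evidence that one without it lacks, so treating the two differently is coherent. Censoring patients just when they look well may also be informative. That last point stands and is a real cost of the fix. The rest does not settle the matter, because the endpoint asks for 24 h of stability and not one reading, and nothing in the SAP says the asymmetry is intended.

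Four stronger readings are tempting and go beyond the text:
- A reader might infer that the SAP declares these discharges not to be improvement. It only codes them as censored, and the protocol's definition counts discharge without exception. The exclusion is the SAP's own.
- A reader might infer that event and censored are equally open to a programmer. They are not: the earliest-of definition favours the event. The main fault is an unsuitable literal result; ambiguity is secondary.
- A reader might take Table 4 to name transfer. It speaks of re-admission; the wording about another hospital is in Tables 7 and 10.
- A reader might infer the same internal conflict in Table 11. It has no discharge rows, so there the hold is left undefined rather than contradicted.

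Table 7 is also somewhat tighter than Table 4, since it asks that the criteria be maintained up to discharge. A single last reading would still pass.

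**Conclusion.** The point holds for Tables 3 and 4 and Tables 6 and 7. Taken literally, one unconfirmed reading followed by a discharge the SAP does not count becomes an event, while the discharge rows would censor the same patient. It concerns only patients who had not completed the 24 h hold before leaving; those who had are properly events.

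Its size cannot be fixed from the documents, which give no rate for such discharges. A count based on every patient with a reading of 2 or less in the day before leaving could include patients who had already completed the hold. On the assumptions shown, the effect is small if these departures are few and balanced (84.9% against 83.8% power at 5% in each arm). It is material only if they differ by arm, for example 83.2% against 73.9% at 5% active and 10% placebo. Nothing in the documents suggests that such an imbalance is expected. This is a correction to make before unblinding, not a threat to the design.

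**What to change.** - In the Table 3 and Table 6 footnotes and row 2 of Tables 4 and 7, state that the rule applies only to discharges that count as events under the residual discharge row. For self-discharge, or discharge with hospital admission or re-admission within 24 h, the censoring discharge rows take precedence unless the 24 h hold was already completed.
- In Table 11, state that such a discharge does not complete the hold, and that the patient is censored at the last vital signs assessment under the existing row for patients who never achieve it.
- Add a sensitivity analysis for TTCI and TTCR that counts these patients as events at the first qualifying reading, and report their number by arm.

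The cost is a sentence in each place and one programming condition on a discharge flag that Tables 4 and 7 already require. There will be a few events fewer and some additional, possibly informative, censoring; the sensitivity analysis would show its effect. Power with the futility rule followed has little to spare at 80.2%, and losing 5% of patients as events would put it at 79.1% on the pessimistic calculation.
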